Study protocol with statistical analysis plan

Fostering Sustainable Dietary Habits Through Optimized School Meals
- an intervention study in Uppsala, Sweden

Date: January 21, 2020

Introduction

Radical changes to food production and consumption are needed to ensure the attainment of Agenda 2030 for Sustainable Development and fulfillment of the Paris Agreement (1). Public school meals have been highlighted as a suitable setting for children to internalize sustainable dietary habits, which may persist throughout life (2). Planning of school meals must take many aspects into account: health promotion, environmental impact, acceptability by the consumers and affordability to those paying for the meals. Currently many schools use organic products, recycle food packaging and aim to reduce food waste, but environmental impacts like greenhouse gas emissions (GHGE) have so far not received much attention.

In Sweden, fully subsidized lunches are served daily in primary schools to all 1.3 million children aged 6 to 15 (3). Due to their reach and scale (approximately 230 million meals/year at an annual cost of around 6 billion SEK), school meals have great potential to increase children's knowledge about health and sustainability, foster sustainable dietary habits and to enable sustainable public procurement.

This study builds on a previously published strategy for how to optimize, plan and implement nutritiously adequate, affordable, acceptable and more climate friendly meals in Swedish primary schools (4). In line with this strategy, the present study aims to: a) Apply linear programming to develop a GHGE-reduced, nutritionally adequate, and affordable four-week lunch menu plan optimized for minimum deviation from the current food supply; and b) evaluate the climate impact of the menu, effects on food waste, food consumption, and pupils' satisfaction with school lunches. Our hypothesis is that school meals can be optimized to be nutritious and more climate friendly, without negatively affecting acceptance, food waste and cost in this context.

Methods

Design

A pre-post design will be used to compare the effect of an optimized menu to the baseline menu on daily food waste and consumption at school level. For a baseline period of four weeks children in primary schools will receive a baseline menu. After a one-week break (winter break), the optimized four-week menu will be served (intervention period).

Recruitment of schools

During the fall of 2019, a meeting was held with the public meal administration in the municipality of Uppsala. The research team described the OPTIMAT project, including the previously developed strategy for optimizing and implementing more climate friendly lunches in schools (4). Following this meeting, the municipality agreed to take part in the project. The municipality's meal planner proposed four primary schools for the study, presently having the highest food related GHGE in public meals in the municipality. To be eligible, the intervention schools were required to have on-site kitchens as well as being able to provide electronic recipes for a standard four-week menu. All proposed schools fulfilled these criteria and approved participation.

Optimization

Recipes for an original (baseline) four-week school lunch menu plan previously served at the recruited schools were obtained through the municipality's electronic meal planning system. The foods included and amounts are considered as the baseline food supply. Each food item included has a code that can be coupled to the Swedish national food database and a national climate database for foods containing life cycle data for each food item (5). This baseline food supply will be optimized using linear programming. The optimized food list, not including new foods or excluding any foods from the baseline list, will be handed to the municipality's meal planner who develops a new menu plan for the intervention using all foods on the optimized list.

Outcomes

To assess the effect of the new menu plan, data on food waste and consumption will be collected daily in each intervention school four weeks before (baseline) as well as during the four-week intervention with a one-week break between measurement periods. Measurements were carried out according to a method for measuring food waste and consumption in school restaurants that was based on School Food Sweden's method for measuring school lunch waste and consumption [1]. The method requires daily weighting (using school kitchen scales) of all food prepared in the kitchen (prepared food); the share of the prepared food that is not eaten and has to be thrown away (serving waste); the share that can be saved (leftover food); and plate waste. The number of plates used daily by the pupils in the school restaurant will also be recorded. These measurements will be made daily by the personnel in the school kitchens during the baseline as well as during the intervention period. Based on these measurements, the total food consumption (kg) will be calculated as the total amount of food prepared in the kitchen (kg) minus the total amount of prepared food that is not eaten and has to be thrown away (serving waste in kg), the total amount of plate waste (kg), and the total amount of leftover food (kg). Plate waste per pupil (g) will be calculated for each day by dividing the total amount of plate waste by the total number of plates used. Similarly, the consumption per pupil (g) will be calculated for each day by dividing the total consumption by the total number of plates used.

Total plate waste, plate waste per pupil, serving waste, total consumption, and consumption per pupil will be considered as the primary outcomes as they are regarded as directly related to the pupils' acceptability of the new menu.

Data on school meal satisfaction will also be collected through an anonymous online questionnaire at baseline and during the last week of the intervention period. Pupils in grades 5 and 8 will answer the questionnaire containing ten questions related to the school lunch. Five of the ten multiple-choice questions specifically cover their general (i.e. not for that specific day of week) sense of satisfaction with the school lunch. The questions include how often they consider that the school lunch tastes good, how many days per week on average they eat it, how often they usually feel full after having eaten lunch, and how often they throw away food. They are also asked to provide an overall rating of the school lunch.

Statistical analysis

A pre-post design will be employed to assess the effect of implementing an optimized lunch menu on daily food waste and consumption at school level. Data will be analyzed by interrupted time series analysis assessing mean and slope differences in daily food waste and consumption between the two periods (6). School lunch satisfaction before and after introduction of the new menu plan will be compared by means of Pearson's χ^2 test.

References

3. The National Food Agency; The Swedish National Agency for Education. *Skolmältiden – en viktig del av en bra skola. (The school meal: an important part of a good school: support and inspiration for school leaders)*. Uppsala, Stockholm; 2013.
5. Floren B, Amani P, Davis J. Climate Database Facilitating Climate Smart Meal Planning for the Public Sector in Sweden. *Int J Food Syst Dyn*.8:72–80.

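### Daily lunch uptake is not an outcome in the time series: the recorded plate count is only a denominator, so the two per-pupil primaries can hold steady or improve while diners fall

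*Combined protocol and SAP*

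**What the plan says.** All of the following is in the combined protocol and SAP.

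- **Outcomes, data collected.** "The number of plates used daily by the pupils in the school restaurant will also be recorded". Prepared food, serving waste, leftovers and plate waste are weighed daily as totals.
- **Outcomes, derived measures.** Plate waste per pupil is obtained by "dividing the total amount of plate waste by the total number of plates used". Likewise, "consumption per pupil (g) will be calculated for each day by dividing the total consumption by the total number of plates used". No other use of the plate count is stated.
- **Outcomes, primaries.** Total plate waste, its per-pupil form, serving waste, total consumption and its per-pupil form "will be considered as the primary outcomes as they are regarded as directly related to the" acceptability of the new menu to pupils. The plate count is not on the list.
- **Outcomes, questionnaire.** "Pupils in grades 5 and 8 will answer the questionnaire" at baseline and in the last intervention week. One of the satisfaction items asks "how many days per week on average they eat it".
- **Statistical analysis.** The interrupted time series is specified as "assessing mean and slope differences in daily food waste and consumption between the two periods". Satisfaction is compared before and after by Pearson's chi-squared test.
- **Introduction, Design and Optimization.** The hypothesis includes no harm to acceptance. The design is pre-post around the winter break, and no control schools are described. The menu is optimised for minimum deviation and neither adds nor drops foods.

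**The concern.** The primaries are chosen to stand for acceptance, and leaving the lunch untaken is a plain form of non-acceptance. The two primaries that look adjusted for the number of diners cannot register it, because they describe only the pupils who took a plate. If those who stop coming are the ones who eat least and discard most, both measures move in the favourable direction as uptake falls.

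The two totals do respond to lost diners, but each mixes the number of diners with the amount per diner. Serving waste has no form adjusted for diners. The series that would show uptake most directly is collected every day in all four schools, yet it has no planned estimate or confidence interval. A conclusion that acceptance was unaffected would then rest on measures that are partly conditional on having accepted the lunch.

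**Working it through.** The documents give no uptake, attendance or gram figures, so there is no stated number to reproduce. The definitions come from the Outcomes section. Every quantity below is an assumption chosen to show direction and range.

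**1. General form.** Let s be the share of diners missing and r their waste (or intake) relative to the average diner.

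- Change in total = −s·r
- Change per plate = (1 − s·r)/(1 − s) − 1

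| s | Total, r=1 | Per plate, r=1 | Per plate, r=0.5 | Per plate, r=1.5 |
|---|---|---|---|---|
| 2% | −2% | 0% | +1.0% | −1.0% |
| 5% | −5% | 0% | +2.6% | −2.6% |
| 10% | −10% | 0% | +5.6% | −5.6% |

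Average eaters can leave without moving either per-plate outcome. Otherwise the direction depends on who leaves.

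**2. Low eaters leave.** Assume 450 diners: 90 who eat 150 g and waste 60 g, and 360 who eat 300 g and waste 20 g.

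- Baseline consumption: (90×150 + 360×300)/450 = 121.5 kg/450 = 270.0 g per plate.
- Baseline plate waste: (90×60 + 360×20)/450 = 12.6 kg/450 = 28.0 g per plate.

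| Diners | Consumption per plate | Plate waste per plate | Total consumption | Total plate waste |
|---|---|---|---|---|
| 441.0 (−2%) | 272.4 g (+0.9%) | 27.4 g (−2.3%) | 120.15 kg (−1.1%) | 12.06 kg (−4.3%) |
| 427.5 (−5%) | 276.3 g (+2.3%) | 26.3 g (−6.0%) | 118.125 kg (−2.8%) | 11.25 kg (−10.7%) |
| 405.0 (−10%) | 283.3 g (+4.9%) | 24.4 g (−12.7%) | 114.75 kg (−5.6%) | 9.9 kg (−21.4%) |

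Both per-plate outcomes and total plate waste look better as diners leave. Total consumption falls, but by less than the number of diners.

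**3. Rejection after taking a plate is captured.** Assume 300 g eaten and 20 g plate waste per diner. If 5% of diners eat half and discard the rest, consumption per plate changes by −0.05×0.5 = −2.5%. Plate waste rises by 0.05×150 = 7.5 g on 20 g, or +38%.

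**4. Serving waste.** Assume 300 + 20 + 30 = 350 g prepared per diner, of which 30 g is serving waste, with no leftovers at baseline. With 5% fewer diners:

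- Kitchens scale preparation: 28.5/30 = −5% in kg, and no change per plate.
- Preparation unchanged, all surplus thrown away: 30 + 0.05×320 = 46 g per baseline diner, or +53% in kg. Per plate, 46/0.95 = 48.4 g, or +61%.
- Preparation unchanged, half the surplus saved: 30 + 8 = 38 g, or +27% in kg.

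Serving waste in kg is hard to read without the number of diners. The per-plate form is stable only where kitchens scale preparation.

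**5. Limit of the plate count.** The documents do not say whether second plates are counted. If second plates fell from 10% to 5% of diners, plates would change by 1.05/1.10 − 1 = −4.5% with no change in diners.

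**The case against.** A reader might infer that uptake is not analysed at all. The documents do not support that. The days-per-week item is listed among the satisfaction questions, and satisfaction has a planned before-and-after test. Nor are lost diners invisible to the primaries: each of the two totals has a per-plate partner, their ratio is the plate count, and total consumption falls in every scenario above. What remains is that the item is self-reported, covers two grades at two time points and is not primary, and that the plan does not set the totals against their per-plate partners. Comparing two fitted results informally gives no interval for the change in diners.

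A reader might also expect a plate-count series to show why diners were lost. It would not. Refusal, absence and season would look the same, and that limit comes from the uncontrolled design and the lack of attendance data.

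Nor is taking no plate the only gap. Food is weighed in total, so a pupil who avoids one dish and eats the same weight of another also leaves the per-plate outcomes unchanged.

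Materiality is also fairly questioned. Aim (b) names waste, consumption and satisfaction rather than participation, the menu changes little by design, and nothing in the documents predicts a fall in uptake. This stands and keeps the severity modest. It does not remove the point, because the hypothesis names acceptance as something to be tested.

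**Conclusion.** The point holds in a limited form. Objective daily uptake is recorded but is not an outcome in the time series. The two per-pupil primaries are conditional on taking a plate and can stay flat or improve while diners fall. Uptake is otherwise seen only through totals that mix diners with amount per diner, and through one self-report item in two grades.

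The size cannot be determined from the documents. With 2% to 10% of diners lost, the per-plate outcomes change by 0% if those missing are average eaters. If they are all low eaters as assumed above, consumption per plate rises 0.9% to 4.9% and plate waste per plate falls 2.3% to 12.7%. These figures rest wholly on assumed intakes, and the real effect may be small. The primaries remain usable. This is an inexpensive improvement to how acceptance is read, not a flaw that invalidates the analysis.

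**What to change.** In the Statistical analysis section:

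1. Add daily plates used as a secondary outcome in the same interrupted time series.
2. Report serving waste per plate alongside kilograms, read together with the plate count, because the per-plate form is stable only if kitchens scale preparation.
3. State that conclusions on acceptance rest on the waste and consumption outcomes together with the plate series and the questionnaire uptake item.
4. State two limits: plates may include second plates; and without attendance data and a control group, a change in plates cannot be attributed to refusal rather than absence or season.

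In the Outcomes section, relabel the two per-pupil measures as per plate.

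The plate count is already recorded, so no new data collection is needed. The cost is one extra secondary outcome, some wording and a little analysis. If the four schools can supply daily attendance, which is an assumption, plates per pupil present would be a useful optional addition.

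### Must the plan say how the four schools enter the interrupted time series and how dependence between school-days is handled?

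*Combined protocol and SAP*

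**What the plan says.** The plan for the primary outcomes is two sentences under Statistical analysis. The first names a pre-post design whose aim is to "assess the effect of implementing an optimized lunch menu" on "daily food waste and consumption at school level". The second reads: "Data will be analyzed by interrupted time series analysis assessing mean and slope differences in daily food waste and consumption between the two periods", with a citation to a tutorial on interrupted time series regression. No model equation, school term, day term, autocorrelation structure or variance estimator is given.

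Four schools take part (Recruitment of schools). The Design section says: "For a baseline period of four weeks children in primary schools will receive a baseline menu"; a one-week winter break follows, then the optimized menu. Optimization refers to a single baseline plan ("Recipes for an original (baseline) four-week school lunch menu plan previously served at the recruited schools were obtained") and a single new one: the meal planner "develops a new menu plan for the intervention using all foods on the optimized list". So the schools appear to share a menu plan in each period and to switch together. Nowhere is it stated that all four serve the same dish on the same date.

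The aim is worded in two ways. Outcomes has "To assess the effect of the new menu plan", which points to this particular menu. Statistical analysis speaks of an optimized menu, which could be read more broadly.

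**The concern.** Four schools measured on the same dates do not supply four independent observations per date if they serve the same dish or share the same weather, holidays or illness. Treating every school-day as independent would overstate the information. Leaving out school differences would do the opposite, mainly for the outcomes in kilograms, which should scale with school size. Positive serial correlation within a school would also make standard errors too small.

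The study hopes to show that a more climate-friendly menu does no harm to acceptance or waste, so the width of the intervals carries much of the conclusion. Too narrow an interval could turn shared day-to-day variation into a menu effect, or give false assurance of no harm. Too wide an interval could hide a real rise in waste. If the schools were analysed one by one, agreement among them could be misread as replication.

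**Working it through.** The plan gives no standard deviation, correlation, significance level or sample size calculation, so it has no figure to reproduce. What can be checked is how much each way of completing the sentence would matter.

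**Inputs from the plan.** Four schools; daily measurement for four weeks before and four weeks during, with a one-week gap.

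**Assumptions.** Five school days a week, so 2 × 4 × 5 = 40 dates and 4 × 40 = 160 school-days, none missing; a two-sided 5% test; equal variances; same-day correlation ρ between schools of 0 to 0.5; no serial correlation except in step 5. The model has intercept, time, level change and slope change. Ratios in steps 1 and 2 are true SE divided by model SE and are the same for level and slope change.

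**1. Stacked, with school intercepts, treated as independent.** Residual df = 160 − 7 = 153. The true variance of a coefficient is proportional to 1 + 3ρ. The model's expected residual variance is [36(1 + 3ρ) + 117(1 − ρ)]/153 = 1 − ρ/17, where 36 = 40 daily means less 4 terms and 117 = 120 within-day contrasts less 3 school terms. Ratio = √[(1 + 3ρ)/(1 − ρ/17)].

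| ρ | 0 | 0.1 | 0.3 | 0.5 |
|---|---|---|---|---|
| Ratio | 1.00 | 1.14 | 1.39 | 1.60 |
| Actual error at nominal 5% | 5.0% | 8.4% | 15.5% | 21.8% |

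If only one pair of schools shares days at 0.5, the ratio is 1.12; with two separate pairs it is 1.23.

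**2. Stacked, without school intercepts.** Let v be the between-school share of variance, with ρ the same-day correlation of what remains. Ratio² = 156(1 − v)(1 + 3ρ) / [36(1 − v)(1 + 3ρ) + 120(1 − v)(1 − ρ) + 120v]. At ρ = 0.3 and v = 0, 0.3, 0.5, 0.7 the ratio is 1.395, 1.206, 1.043, 0.828. Setting it to 1 gives v = 4ρ/(1 + 4ρ), that is 0.29, 0.55 and 0.67 at ρ = 0.1, 0.3 and 0.5. Beyond those shares the SE is too large, so the direction of error reverses.

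**3. One daily series, summed or averaged over schools.** The variance of a daily mean, (1 + 3ρ)/4, is what the residuals estimate. The ratio is 1.00 at every ρ.

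**4. Separate school series.** Each school's error stays at 5.0%. By simulation, the chance of two or more schools being significant in the same direction with no effect is 0.71%, 1.16%, 2.12% and 3.35% at ρ = 0, 0.1, 0.3 and 0.5.

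**5. Serial correlation.** With school intercepts, ρ = 0 and within-school AR(1) of 0.1, 0.2, 0.4 or 0.6 ignored, the model SE of the level change is 0.91, 0.83, 0.68 or 0.54 of the true one, and the error is 7.4%, 10.4%, 18.3% or 29%.

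**6. Inference to these two menus only.** Dish-to-dish variation is then part of the effect, not sampling error. If all same-day variance is dish, the true variance of a daily mean, for the mean difference, is (1 − ρ)/4. At ρ = 0.1, 0.3, 0.5:
- the stacked model assumes 1/4, so its SE is too large by 1/√(1 − ρ) = 1.05, 1.20, 1.41;
- the daily-mean model assumes (1 + 3ρ)/4, so its SE is too large by √[(1 + 3ρ)/(1 − ρ)] = 1.20, 1.65, 2.24.

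If a fraction f of the same-day variance is not dish, the stacked model is right when fρ + (1 − ρ)/4 = 1/4, that is f = 1/4.

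**The case for a change.** The best case for a change is that it costs only wording and no data. The school-level phrase names the unit of measurement, not how four units combine, and citing a tutorial fixes no choice. With five primary outcomes and a no-harm aim, an open choice can be settled after the results are seen, and steps 1, 2 and 5 show that it can matter. The algebra stands, and so does the observation that the text is silent.

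What does not follow is that the plan is wrong. It nowhere commits to treating school-days as independent, and the single daily series in step 3 is as plain a reading as any. The replication worry in step 4 is small, and the plan never proposes to count significant schools.

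Nor is there one clearly better model to write in. Segmented regression on daily across-school means, with weekday terms and a small-sample-corrected AR(1), is a sound option for inference to optimized menus in general. At serial correlation 0.5, however, it leaves about 5 df and intervals 2.4 to 3.4 times as wide as the stacked ones. For these two menus only, step 6 shows it may overstate the uncertainty more than the model it replaces. That is a trade-off on which statisticians can differ.

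**Conclusion.** The concern describes missing detail, not an error, and no change to the plan is called for. The possible distortion runs from none (one daily series, or no shared-day correlation) to an error near 22% at same-day correlation 0.5, or 29% at within-school AR(1) of 0.6. It has the opposite sign if school intercepts are left out and schools differ greatly. Each of these figures needs a model the plan does not state together with a correlation the documents do not give; the same-day ones also need day effects shared between schools, and a common dish on each date is inferred, not stated. The 5% level and five-day week are assumed too. Whether the cited tutorial settles serial correlation cannot be judged from the documents. An analyst fitting an interrupted time series to four schools would have to decide how they enter and would ordinarily examine autocorrelation. Sensible ways of doing so fit the text as written.

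### With no weekday term specified, a pattern that rises or falls through the school week biases the step at the menu switch, though not the slope change or the period-mean difference

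*Combined protocol and SAP*

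**What the plan says.** The primary analysis is described in one sentence of the Statistical analysis section: an "interrupted time series analysis assessing mean and slope differences in daily food waste and consumption between the two periods", with a reference to a published tutorial. It names no weekday or other periodic term, school term, treatment of serial correlation or standard-error method. It also does not say whether the mean difference is the step at the switch or the contrast of the two period means.

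The data are daily and school-level. The Design section says: "For a baseline period of four weeks children in primary schools will receive a baseline menu". It continues: "After a one-week break (winter break), the optimized four-week menu will be served". The Recruitment section gives four schools. The Outcomes section lists five primary outcomes: three of waste and two of consumption.

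**The concern.** Equal numbers of each weekday in the two periods look like full protection, but they protect only some of the estimates. Within each week Monday always comes first and Friday last, so a pattern that climbs or falls through the week is correlated with time inside each period. Both fitted lines tilt in the same direction. The baseline ends on a Friday and the intervention starts on a Monday. With a late-week rise, the baseline line is therefore projected too high at the switch and the intervention line starts too low, and a drop appears without any menu effect.

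The study hypothesis is that the new menu does no harm to acceptance, waste or cost. For waste, a late-week rise would hide a real worsening and a Monday peak would create a false one. For consumption, where a fall is the bad direction, the consequences are the other way round. The bias is a fixed feature of the design, so more schools would not average out a weekday pattern that they share.

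**Working it through.** The plan states no SD, effect size, power or sample-size figure, so there is none to reproduce. The check puts a pure weekday pattern through the segmented regression (intercept, time, period, period × time).

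**Inputs.** From the Design section: four weeks, a one-week break, four weeks. Assumed: five school days in every week, hence 20 + 20 days. Weekdays are numbered k = 0 (Monday) to 4 (Friday), with pattern p_k.

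**Formula.** Let S = Σ(k−2)p_k. The tilt of each fitted line is 4S / SS, where SS is the sum of squares of time about the period's own mean. Both lines tilt equally, so the step is biased by −D × 4S / SS, where D is the distance between the period midpoints.

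- Consecutive school days: SS = 20 × (20² − 1)/12 = 665; D = 20.
- School days with the five-day break counted: SS = 665; D = 25.
- Calendar days: SS = 5 × 49 × 5 + 4 × 10 = 1265; D = 35.

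**Patterns.** A Friday-only effect of size 1 has S = 2 and SD = √0.16 = 0.40. A Monday-only effect has S = −2 and the same SD. A linear rise with Monday–Friday range 1 has S = 2.5 and SD = √0.125 = 0.354. Any pattern symmetric about Wednesday has S = 0.

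Example, Friday peak with consecutive days: −20 × 4 × 2 / 665 = −0.241, and −0.241 / 0.40 = −0.60.

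| Step bias per weekday SD | Consecutive | Break counted | Calendar |
|---|---|---|---|
| Friday peak | −0.60 | −0.75 | −0.55 |
| Steady rise | −0.85 | −1.06 | −0.78 |
| Monday peak | +0.60 | +0.75 | +0.55 |
| Symmetric about Wednesday | 0 | 0 | 0 |

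**What is not biased.** The tilts are equal, so the slope change has bias 0. Each weekday appears four times in each period, so the difference in period means also has bias 0. Both results need complete weeks.

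**Illustrative size (assumption).** If weekdays explain a share s of daily variance, the weekday SD is √s daily SDs. With consecutive coding and s = 10/20/30%, the step bias is −0.19/−0.27/−0.33 daily SD for a Friday peak and −0.27/−0.38/−0.47 for a steady rise.

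**Standard errors, independent days.** For one 40-day series with four coefficients and a pattern not absorbed by the slopes, reported over true SE is √[1 + (40/36) × s/(1−s)]. At s = 10% this is √1.123 = 1.06, and at 30% it is √1.476 = 1.21.

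**Standard errors, correlated days.** A simulation of one 40-day series with first-order autoregressive errors and ordinary least squares gave these ranges of reported over true SE across the four coefficients:

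- s = 10%: 0.94–0.96 at lag-1 correlation 0.1; 0.77–0.80 at 0.3.
- s = 30%: 0.96–1.01 at correlation 0.2; 0.88–0.93 at 0.3.

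With Newey–West errors at s = 30% and no correlation, the ratio was 1.06–1.11 at lag 1, 0.93–0.99 at lag 3 and 0.80–0.83 at lag 5.

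**Cost of weekday terms.** They remove the within-week part (2 × 4 × 10 = 80) from the information on the common slope. With consecutive days this falls from 2 × 665 = 1330 to 1250. With the switch at the first intervention day, the step variance (in units of residual variance) goes from 0.1 + 400/1330 + 0.001 = 0.402 to 0.1 + 400/1250 + 0.001 = 0.421. The SE ratio is √(0.421/0.402) ≈ 1.02. The other two time scales give 1.3% (calendar) and 2.5% (break counted). The slope-change SE is unchanged at equal residual variance.

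**The case against.** The strongest objection is that the plan never names a step. Read literally, it compares means and slopes between periods, and whole weeks leave both differences unbiased. That stands as a limit on the point. It does not dispose of it, because an interrupted time series commonly reports a step and the plan does not say which quantity it means.

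The model is also known only from one summary sentence and a tutorial that is not reproduced. The fair statement is that no weekday term is specified, not that one has been ruled out. Whole Monday-to-Friday weeks are likewise an inference.

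A reader might infer that every standard error will be too wide. The documents do not support that: the plan names no standard-error method, and modest positive serial correlation is enough to make ordinary least-squares errors too narrow.

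A reader might also look for evidence of a weekday effect in the documents. The questionnaire's reference to a "general (i.e. not for that specific day of week) sense of satisfaction" only clarifies that pupils rate lunch in general. The leftover definition, "the share that can be saved (leftover food", contains no weekend rule. Neither shows that waste or consumption varies by weekday.

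Finally, weekday indicators remove only a pattern common to both periods. Each weekday occurs four times per period on a four-week menu, so the dishes themselves can shift the apparent pattern. That is a real limit of the remedy.

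**Conclusion.** The point holds in conditional form. If the step at the switch is reported, if weeks are complete Monday-to-Friday weeks, and if the outcome trends through the week, the step is biased. With consecutive-day coding the bias is about 0.60 weekday SDs for a Friday or Monday peak and 0.85 for a steady rise; counting the break makes it larger and calendar coding slightly smaller. It is zero for a pattern symmetric about Wednesday. The slope change and the period-mean difference are unbiased when no days are lost.

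Because the documents give no weekday variance, neither the size nor the direction for this trial can be stated. It would be wrong to conclude that the plan favours the new menu, since a Monday peak in waste works against it. The effect on standard errors is likewise conditional: too wide under ordinary least squares with otherwise independent days, and possibly too narrow otherwise. The case for change rests on cheap protection for five primary outcomes, not on a demonstrated weekday effect.

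**What to change.** Specify the model for all five primary outcomes as: outcome = school + weekday + time + period + period × time, with four indicators for Tuesday to Friday against Monday. State whether the mean difference is the step at the switch or the contrast of period means, and take that quantity and the slope change from this model. If school days are lost unevenly, the same terms also correct the resulting weekday imbalance in the period means. Weekday terms do not settle serial correlation, so the standard-error method should be stated alongside.

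The cost is a sentence or two in the Statistical analysis section and no new measurements, since the data are recorded daily. It uses 4 degrees of freedom. If there is no weekday pattern, the step's standard error rises by about 1–2.5% and the slope change's not at all, apart from the lost degrees of freedom. A weekday pattern that differs between the two periods would remain uncorrected.
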